## Abbreviations

ALPHA	A young people's research advisory group
BRTC	Bristol Randomised Trial Collaboration
CACE	Complier Average Causal Effect
CAMHS	Child and Adolescents Mental Health
	Services
DECIPHer	Centre for the Development and Evaluation
	of Complex Interventions for Public Health
	Improvement
FG	Focus group
FREC	Faculty Research Ethics Committee
FHSEC	Faculty of Health Sciences Ethics Committee
FSM	Free School Meal status
HSC	Healthy Schools Coordinator
ICC	Intraclass Correlation
ID	Identity
INSET	IN-SErvice Training
LA	Local Authority
MICE	Multivariate Imputation by Chained
	Equations
MHFA	Mental Health First Aid
MAR	Missing At Random
MRC	Medical Research Council
Ofsted	Office for Standards in Education
OECD	Organisation for Economic Co-Operation and
	Development
PHQ-8	Patient Health Questionnaire 8 item
PI	Principle Investigator
PMG	Project Management Group
PS	Peer supporter
Participant	An individual who takes part in a trial
NIHR	National Institute for Health Research
NIHR PHR	National Institute for Health Research Public

	Health Research
RCT	Randomised Controlled Trial
SAE	Serious Adverse Event
SDQ	Strengths and Difficulties Questionnaire
SHRN	School Health Research Network
SLT	Senior leadership teams in schools
SL	Senior leaders in schools
STARS	Supporting Teachers and Children in
	Schools
ТО	Baseline data collection period
T1	Follow up data collection period, 12 months
	after baseline
T2	Follow up data collection period, 24 months
	after baseline
TSC	Trial Steering Committee
WISE	Wellbeing in Secondary Education
WEMWBS	Warwick Edinburgh Mental Wellbeing Scale
WPAI	Work Productivity and Activity Impairment
	Questionnaire
YMHFA	Youth Mental Health First Aid

## **1. INTRODUCTION & PURPOSE**

This document details the rules proposed and the presentation that will be followed, as closely as possible, when analysing and reporting the main results from the WISE study: A cluster randomised trial of a mental health training and support intervention provided to secondary school teachers. The purpose of the plan is to:

- 1. Ensure that the analysis is appropriate for the aims of the trial, reflects good statistical practice, and that interpretation of a priori and post hoc analyses respectively is appropriate.
- 2. Explain in detail how the data will be handled and analysed to enable others to perform the actual analysis in the event of sickness or other absence

Additional exploratory or auxiliary analyses of data not specified in the protocol are permitted but fall outside the scope of this analysis plan (although such analyses would be expected to follow Good Statistical Practice).

The analysis strategy will be made available if required by journal editors or referees when the main papers are submitted for publication. Additional analyses suggested by reviewers or editors will, if considered appropriate, be performed in accordance with the Analysis Plan, but if reported the source of such a post-hoc analysis will be declared.

Amendments to the statistical analysis plan will be described and justified in the final report of the trial.

## 2. SYNOPSIS OF STUDY DESIGN AND PROCEDURES

The information in these sections has been extracted from the protocol on 18 May 2016 in order to place the analysis plan within the context of the trial aims and methods.

#### 2.1. Trial objectives and aims

#### 2.1.1. Primary objective

To establish if the WISE intervention leads to improved teacher emotional wellbeing compared to usual practice.

## 2.1.2. Secondary objectives

 Does the WISE intervention lead to lower levels of teacher depression, absence and presenteeism, improved student wellbeing, attendance and attainment, and reduced student mental health difficulties compared to usual practice?

- Do any effects of the intervention differ according to the proportion of children receiving free school meals (FSM – an indicator of the socioeconomic catchment area) and geographical area, or individual level baseline mental health, gender, ethnicity and FSM?
- 3. What is the cost of the WISE intervention, and is it justified by improvements to staff and student wellbeing and reductions to staff depression and student difficulties?
- 4. Does the WISE intervention work according to the mechanisms of change hypothesised in the logic model?
- 5. Is the WISE intervention sustainable?

## 2.2. Trial design and configuration

This is a cluster randomised controlled trial, with schools as the unit of allocation.

## 2.3. Trial centres

The study will be conducted within two geographical areas (Bristol/ surrounding areas of Bristol and South Central/ South East Wales).

## 2.4. Eligibility criteria

## 2.4.1. Cluster inclusion criteria

All state mainstream secondary schools within the relevant geographical areas.

## 2.4.2. Cluster exclusion criteria

- I. Fee paying schools
- II. Special schools (e.g. for those with learning disabilities)
- III. Pupil referral units
- IV. Schools that were pilot schools
- V. Schools already participating in other, similarly intensive, research studies (healthy schools teams will advise on this)
- VI. Schools that have already provided or are providing MHFA training to teachers
- VII. Schools that do not have FSM data
- VIII. Schools in the same academy chain and LA as another participating school

## 2.4.3. Individual inclusion criteria

All staff who are in teaching posts.

## 2.4.4. Individual exclusion criteria

All staff who are in non-teaching posts.

## 2.5. Description of interventions

Each intervention school will receive the following:

- Staff peer support service: 8 % of staff who are nominated via confidential voting of questionnaire respondents will be selected (ensuring a mixture of gender and years of experience and (non)teaching role) and will receive 2 day MHFA training. Then will act as peer supporters to other staff members.
- INSET teacher training using MHFA for schools and colleges: Another 8 % of teachers only (targeted at tutors or heads of year) who did not receive the 2 day MHFA training, will receive one day youth MHFA course. The learning will be applied during usual interactions with students.
- Mental health awareness raising session: One hour training for all teachers, during in-service training or meeting time, that will introduce the intervention and focus on the importance of mental health issues in school.

Control schools will continue with usual practice.

## 2.6. School Selection and Randomisation procedures

Secondary schools within each country will be organised into four areas (Bristol / surrounds of Bristol in England and South East / South Central in Wales). Within each area grouping, the schools will be stratified into three levels according to FSM (high, medium and low). In Wales, two schools will be randomly selected from each stratum in each area; this will be conducted by statisticians blinded to any identifying information. In England, all schools will be invited for expressions of interest to participate, and where more than two in each stratum respond, two will be randomly selected. If it is not possible to obtain consent to participate from 2 schools within one FSM stratum then it will be joined to another stratum and 4 schools will be picked from that stratum. For example if 2 high FSM schools cannot be recruited, then high and medium FSM strata will be joined and 4 schools selected from this new stratum.

The schools that have been selected to participate in the trial (as described above) will be randomly allocated to either the control or intervention arm of the trial stratified by geographical region (Bristol area of England, and South East/South Central Wales) and FSM level (high, medium or low).

#### 2.7. Sample size and justification

The primary outcome measure will be the WEMWBS scale. A change of 3 points on this scale is close to the difference in mean scores between the highest and lowest ranked schools in the pilot study. The sample size takes account of clustering; in the pilot data from 6 schools, the WEMWBS ICC (calculated using the loneway command in Stata) for teachers was 0.01 (95%Cl 0.00, 0.05) [1]. We assume a mean of 50 teachers followed up per school after allowance for 20% dropout (with a coefficient of variation of sample size of 0.5), and an SD for WEMWBS of 8.4 (based on the pilot data). Given that estimates based on pilot data can be unreliable [2], assuming an ICC of 0.05, which is greater than that seen in the pilot, -a sample size of 24 schools (12 intervention and 12 control) would achieve over 80% power. This would rise to 98% if the ICC is 0.02, and fall to 68% for an ICC of 0.08. These estimates of power are likely to be conservative given that the sample size calculation does not account for the baseline assessment of the outcome.

#### 2.8. Blinding and breaking of blind

Allocation to study arm will take place after baseline data are collected to ensure blinding among all parties during this first data collection. It is not possible for the schools, teachers or students to be blind to intervention status. The research assistants/associate leading the outcome data collection, will also be collecting the process data which will prevent blinding. The schools will however be assigned ID numbers and as such casual staff and the statisticians analysing the primary and secondary outcomes data will be blind to the schools' identities and intervention status. A timeline diagram of blinding status throughout the trial processes will be produced for clarification [3].

#### 2.9. Trial committees

The study team will hold 2-4 monthly Project Management Group (PMG) meetings, along with the researchers, statisticians and health economists working on the project, and two members of the public (teachers) to plan each phase of the study.

The Trial Steering Committee (TSC) will be made up of an independent chair with statistical and trial expertise, the study PI, a co-applicant from the Cardiff site, an independent statistician, two further independent scientists with relevant expertise and the Head of Research and Policy at the Education Support Partnership. Meetings will also be attended by other co-applicants or study team members as necessary. The TSC will monitor trial progress and conduct, and advise on scientific credibility. It will meet annually throughout the study, with teleconference and email contact in the interim as necessary.

## 2.10. Outcome measures

## 2.10.1. Primary outcome

The primary outcome is the average effect of the intervention on mental wellbeing of teachers over the duration of follow up, measured using the self-completed WEMWBS questionnaire [4] collected at baseline, one and two year follow ups. The WEMWBS scales from 14-70 and will be analysed as a continuous variable.

## 2.10.2. Secondary outcomes

Time averaged treatment effects will be reported for those variables collected at baseline, one and two year follow ups:

- Teacher depression measured by PHQ-8 [5] that scales from 0 to 24
- Teacher presenteeism measured by WPAI [6], that scales from 0 to 10
- Teacher absence (ever/never in the past 4 weeks) and total number of days of absence, which will be collected at baseline, one and two years follow up by self-report

Adjusted difference between trial arms at 2 years follow up will be reported for those variables collected only at baseline and two year follow up:

- Student mental wellbeing measured by the WEMWBS
- Student psychological distress, measured by the SDQ [7] that scales from 0 to 40
- Teacher absence collected from schools' routine data sources
- Teacher retirement/resignation collected from schools' routine data sources
- Student attendance (%) for all year groups

Year 11 attainment (percentage achieving five or more grades 5-9 GSCEs including English and Maths)

Teacher PHQ-8 and student WEMWBS and SDQ will be measured as continuous variables. PHQ-8 will also be measured as an ordinal variable (a score of 0-4 indicating no depressive symptoms / 5-10 indicating mild symptoms / 10-14 indicating moderate symptoms / 15-19 indicating moderately severe symptoms 20-24 indicating severe) and a binary variable, with a cut-point of 10 or more indicating depression. Teacher absence and presenteeism will be treated as binary (any vs no absence in the previous four working weeks and health problems having 0 effect vs 1-10 effect on work over the previous four working weeks) to ascertain the impact of the intervention on any absence or presenteeism. Teacher absence will also be categorised as 0 / 1 day or less / 2 -7 days / more than 7 days, and the categories for teacher presenteeism will be 0 / 1-5 / 6-10. Teacher absence and teacher retirements/resignations as reported by schools, student attendance and

student attainment (% students achieving five or more 5-9 grade GCSEs including English and Maths) will all be reported at a school level and will be treated as continuous variables.

	Baseline	Year 1	Year 2
Teacher	WEMWBS	WEMWBS	WEMWBS
	PHQ-8	
 
PHQ-8
 
	• PHQ-8
	Presenteeism	Presenteeism	Presenteeism
	• Teacher absence (past 28	Teacher absence	Teacher absence (past 28
	days)	(past 28 days)	days)
Student	- WEMWBS		- WEMWBS
	- SDQ		- SDQ
School	- Teacher absence (%)		- Teacher absence (%)
-	- Retirement/resignation		- Retirement/resignation
Teacher			
School	- Attendance (%)		- Attendance (%)
-	- Attainment (%)		- Attainment (%)
Student			

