## Table 6. Secondary endpoints summary

		Control			Intervention	
Variables (Teachers) :	Ν	Mean/%	SD	Ν	Mean/%	SD
PHQ-8 Score (T2)						
Average days absent past 4 weeks (T2)						
Presenteeism Score (T2)						
Absence (ever/never) (T2)						
Teacher absence (school level)						

		Control			Intervention	
Variables (Students) :	Ν	Mean/%	SD	Ν	Mean/%	SD
SDQ score						
Student WEMWBS score						
Student absence (school level)						
Attainment (school level)						

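### Time-averaged effects are promised for the 0-10 presenteeism score and total days absent, but only any-versus-none and banded analyses are defined, so neither gets an effect estimate on its own scale

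*SAP*

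**What the plan says.** Section 2.1.2 asks whether the intervention leads to "lower levels of teacher depression, absence and presenteeism".

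Section 2.10.2 opens its list of repeatedly measured outcomes with "Time averaged treatment effects will be reported for those variables collected at baseline, one and two year follow ups". Two items on that list are "Teacher presenteeism measured by WPAI [6], that scales from 0 to 10" and "Teacher absence (ever/never in the past 4 weeks) and total number of days of absence". Total days stands beside ever/never, so it reads as an outcome in its own right.

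The same section then fixes the form of each variable:

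- At individual level, only teacher PHQ-8, student WEMWBS and student SDQ are declared continuous. PHQ-8 is also given ordinal and binary forms.
- Presenteeism is binary, "health problems having 0 effect vs 1-10 effect on work over the previous four working weeks", and banded as 0, 1-5 and 6-10.
- Self-reported absence is binary (any or none over four working weeks) and banded as none, up to 1 day, 2 to 7 days, and over 7 days.
- Teacher absence taken from school records is a separate, school-level outcome and is treated as continuous.

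Section 6.3 chooses a linear, ordinal or logistic model by the type of variable and names no count or two-part model. Table 8 gives self-reported absence and presenteeism binary and ordinal odds-ratio rows only. The presenteeism score and mean days absent appear in Table 1 (baseline) and Table 6 (T2) as N, mean and SD by arm.

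**The concern.** The list of outcomes and the list of analyses do not agree. An analyst who follows section 2.10.2, section 6.3 and Table 8 as written will produce no effect estimate or interval for two quantities that the SAP names as outcomes.

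The substitutes answer a narrower question. The binary form asks whether a teacher is affected at all. The banded form asks whether a teacher crosses one of a few thresholds. Neither responds to a change inside a band. The trial could therefore report odds ratios near 1 while the descriptive means in Table 6 differ between arms. Readers would then have no interval, adjusted for clustering and stratification, with which to judge that difference, and Table 6 covers T2 only.

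The SAP gives no reason for treating these two outcomes differently from PHQ-8, which sits in the same sentence of the objective.

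**Working it through.** **1. What is promised and what is defined**

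| Teacher outcome (self-report) | Effect promised, 2.10.2 | Own scale | Bands | Binary |
|---|---|---|---|---|
| PHQ-8 | time-averaged | yes | yes | yes |
| Presenteeism, 0-10 | time-averaged | no | yes | yes |
| Total days absent | time-averaged | no | yes | yes |

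**2. What each form can see**

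| Change in one teacher | Binary | Bands | Own scale |
|---|---|---|---|
| Presenteeism 8 to 2 | unchanged | moves from 6-10 to 1-5 | falls by 6 |
| Presenteeism 5 to 1 | unchanged | unchanged | falls by 4 |
| Absence 7 to 2 days | unchanged | unchanged | falls by 5 |

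This follows from the definitions and needs no assumption.

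**3. Effective sample size, checked against the SAP's own power figures**

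The only power statement is in section 2.7, for the primary outcome. Its inputs are a 3-point difference, SD 8.4, 12 schools per arm, mean cluster size m = 50 and CV of cluster size 0.5. I assume a two-sided 5% level.

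- Teachers per arm: 12 × 50 = 600.
- Design effect: 1 + [(1 + CV²)m − 1] × ICC = 1 + 61.5 × ICC.
- Effective n per arm: 600 / design effect.
- Power: noncentral t with 24 − 2 = 22 df and noncentrality 3 / [8.4 × √(2/n)].

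| ICC | Design effect | Effective n per arm | Power, recomputed | Power, SAP |
|---|---|---|---|---|
| 0.02 | 2.230 | 269 | 97.7% | 98% |
| 0.05 | 4.075 | 147 | 83.4% | over 80% |
| 0.08 | 5.920 | 101 | 68.1% | 68% |

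The SAP's figures reproduce. Effective n of 147 and 269 per arm are carried forward.

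**4. Illustration with assumed distributions**

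The SAP gives no distribution for presenteeism or days absent, so everything below is assumed and refers to one wave. Power is by normal approximation: a difference in means for the graded form, and a rank test for the bands, which is close to a proportional-odds test.

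*Presenteeism.* The share scoring zero is 30% to 60%. Scores 1 to 10 have probabilities falling by a factor exp(−0.22) per point. Scenario A: 60% of teachers scoring 3, 4, 5, 8, 9 or 10 drop 2 points, all within a band. Scenario B: every score of 2 or more drops 1 point.

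| Scenario | Zero share | Mean score | Power on mean, n = 147 / 269 | Bands, n = 147 / 269 | Binary |
|---|---|---|---|---|---|
| A | 30% | 2.67 to 2.28 | 25% / 40% | 5% / 5% | 5% |
| A | 60% | 1.53 to 1.30 | 13% / 20% | 5% / 5% | 5% |
| B | 30% | 2.67 to 2.13 | 44% / 68% | 9% / 13% | 5% |
| B | 60% | 1.53 to 1.22 | 21% / 35% | 6% / 6% | 5% |

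The 5% entries are the false-positive rate: nothing visible to that form has changed. In scenario B a rank test on the full 0-10 range has power 31% / 51% at 30% zeros and 8% / 11% at 60%. It recovers less than the mean.

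*Absence.* The share with no absence is 60% to 80%. Days 1 to 20 have probabilities falling by a factor 0.75 per day. Absences of 4-7 days are cut to 2, and those of 10 or more to 8. At 60% zeros, mean days go from 1.57 to 1.08, and (1.57 − 1.08)/1.57 = 31%. The four bands hold 60.0%, 10.0%, 24.7% and 5.2% both before and after. Power on mean days runs from 42% (60% zeros) down to 21% (80% zeros) at n = 147, and from 66% down to 34% at n = 269. Both planned forms stay at 5%.

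**The case against.** Several points on the other side stand in whole or in part.

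- **The binary question is deliberate.** Section 2.10.2 says it is there to learn the effect on any absence or presenteeism. That is a legitimate prespecified question and should stay.
- **Severity is coarsened, not ignored.** The ordinal models register moves across a band edge, such as 8 to 2. This limits the point to changes within a band.
- **Absence has partial cover.** School-reported teacher absence is modelled as continuous. However, it comes from routine records, has one value per school for 24 schools, and is compared only at year 2 with baseline adjustment. It does not analyse self-reported days. Presenteeism has no such cover.
- **Table 8 may be an incomplete shell.** It also has no row for retirement/resignation, which section 2.10.2 treats as continuous. But section 2.10.2 itself leaves the score and days out of its continuous variables, and section 6.3 picks the model by variable type. If a continuous analysis was intended, the text needs to say so.

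A reader might infer that the plan fails its stated objective because that objective is a fall in severity or duration. The SAP says only "lower levels of teacher depression, absence and presenteeism", and fewer teachers affected, or fewer in the top band, would also answer it.

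A reader might also infer that the graded analyses would be well powered and the planned ones nearly powerless. The illustrations do not show that. They are built around changes the binary form cannot see, and even the graded test reaches only 13% to 44% at the planning ICC of 0.05.

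**Conclusion.** The point holds as a mismatch inside the SAP. Time-averaged effects are promised for the 0-10 score and for total days, but none is planned on either scale, and within-band change is invisible to both planned forms. This rests on the text alone.

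The size of the loss cannot be fixed from the SAP. Under the assumed distributions, mean days absent can fall 31% with no change in any band. For presenteeism, a 1-point fall in all scores of 2 or more gives power of 21% to 44% on the mean score against 6% to 9% for the bands (ICC 0.05). If an effect mainly moves teachers across band edges or to zero, the planned forms will pick much of it up and the loss is smaller.

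The consequence is limited to two secondary outcomes; the primary analysis is untouched. It would be tempting to say that the graded forms should replace the binary and banded ones as lead analyses. The SAP does not support that: the binary question is prespecified with a reason, and the order is a matter of judgement.

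**What to change.** 1. In section 2.10.2, state that the presenteeism score and total days of self-reported absence will also be analysed on their own scales.
2. In section 6.3, add a time-averaged arm comparison for each, with the same repeated-measures and school clustering structure and the same three adjustment models:
   - for the score, a linear mixed model or an ordinal mixed model over the full 0-10 range, chosen in advance;
   - for days, a negative-binomial, two-part or robust-standard-error model suited to many zeros.
3. In Table 8, add matching rows with 95% confidence intervals: a mean difference (or full-range odds ratio) for the score, and a ratio or difference in days.
4. Keep the binary and banded analyses as prespecified. If part-days are recorded, also assign values between 1 and 2 days to an absence band; at present 1.5 days has none.

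The cost is SAP wording and two further outcome analyses on data already due to be collected. The downside is two more secondary tests, and skewed data that need a suitable model and a check of fit.

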## **3. GENERAL ANALYSIS CONSIDERATIONS**

## 3.1. Analysis datasets

Full Analysis set: All teachers who are in post and all students in the appropriate year group who are on the register, in the randomised schools, during at least one of baseline, one or two year data collection, will form the main analysis sample. It is analysis of this sample which is in accordance with the "intention to treat" (ITT) principle.

Per protocol set: All participants in the Full Analysis set who are from schools with no major protocol violations that could interfere with the objectives of the study.

ITT will be used as primary outcome, then as sensitivity we will use ITT and impute missing data, and we will also present per protocol analysis, as well as CACE analysis.

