## 6.2. Primary analysis

The tested null hypothesis is that there is no difference in level of teacher wellbeing over the period of 2 years (i.e. repeated measures analysis, no primary timepoint) in schools with peer supporters that have MHFA training and those in schools that do not have such support. The primary analysis will be carried out under the intention to treat principle, analysing participants as randomised without the imputation of missing data.

- 1. The primary analysis: Repeated measures (random effects) models will be used to examine pattern of change in primary outcome over baseline, T1 and T2, adjusted for stratification variables, sex and years of experience. This will include a random effect for individual participants, and another for school. If models fail to converge, we will use robust standard errors to account for clustering at one of the levels. This model will include every teacher who has at least one measure of the outcome (i.e. at baseline, one or two year follow up). Using a maximum likelihood estimator this analysis is robust to data which are MAR [8, 9].
- 2. Results will be presented as mean difference in the primary outcome between the trial arms over the follow up period, with associated 95% confidence interval and p- value.

Assumptions and Links for each model:

The link function for this model will be the identity function, and the different model assumptions will be checked to ensure that the model is a good fit for the data. This will include, check for normality assumptions at the different levels, making sure that homoscedasticity holds, and checking that the assumption of linearity of change holds. If these assumptions do not hold, we will investigate transformations of the data to achieve normality. If the model does not converge, we will use a simpler random effects model accounting for clustering by school only.

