## 6.4. Sensitivity analysis

The sensitivity of the results to the assumptions about the missing data will be assessed using multiple imputation for missing outcome data. This will include imputing under a range of assumptions about the missing data mechanism – allowing the missing data mechanism to depend on the unobserved outcome data, the arm of the trial, and both. We will assess the impact of non-response and missing data on teacher WEMWBS and PHQ-8 outcomes and student WEMWBS and SDQ outcomes. The sensitivity of conclusions to late returned questionnaires will also be checked, by repeating the analyses with only those questionnaires returned within 2 days of the initial data collection date. We will also re-run the primary analyses without identified outliers, as well as those without major protocol violation to assess the effect of outliers and protocol violation on the main outcome.

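### The per-protocol re-run drops whole schools after randomisation and has nothing to correct the imbalance this may create, so it is open to bias of unknown direction

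*SAP*

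**What the plan says.** Section 3.1 defines the per-protocol set as those members of the Full Analysis set "who are from schools with no major protocol violations that could interfere with the objectives of the study". The unit of exclusion is the school. The SAP does not say which violations are major (the heading at 5.3 has no text under it); the protocol may.

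Section 3.1 makes ITT primary and adds, as sensitivity work, that "we will also present per protocol analysis, as well as CACE analysis". Section 6.4 re-runs the primary analyses without outliers, "as well as those without major protocol violation to assess the effect of outliers and protocol violation on the main outcome". Table 9 gives the per-protocol result its own row, with a confidence interval and p-value.

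The model being re-run is in Section 6.2: baseline, T1 and T2 WEMWBS as repeated outcomes, random effects for teacher and school, "adjusted for stratification variables, sex and years of experience". Section 6.3 adds a treatment-by-time interaction only as a secondary analysis, which implies a single arm term across all three waves in the primary model.

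Section 2.5 gives intervention schools three components: a peer support service staffed by 8% of staff, one-day training for another 8% of teachers, and an awareness session for all teachers. For the other arm it says "Control schools will continue with usual practice".

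**The concern.** Randomisation balances school wellbeing between the arms in expectation for the 24 schools as allocated. It does not do so for a subset chosen by what happened after allocation. An intervention school can fall short on training, the peer service or the awareness session; a control school has nothing to deliver. If schools that deliver well also tend to have higher (or lower) staff wellbeing anyway, removing the others shifts the intervention mean even when the intervention has no effect.

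Nothing in the re-run corrects for this. Baseline WEMWBS is one of the outcomes and not a covariate, and a single arm term over all waves takes up any standing school difference in full. What is at stake is the reading of one sensitivity row: a per-protocol estimate above the ITT estimate could be taken to show that full delivery works, when school selection alone could produce it. The row also has less power.

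**Working it through.** **Plan's own figure.** Inputs from SAP 2.7: difference 3, SD 8.4, mean 50 teachers per school, coefficient of variation 0.5, 12 schools per arm. Two-sided 5% is assumed from the 95% interval in 6.2.

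- Design effect = 1 + ((1 + 0.5²) × 50 − 1) × ICC. At ICC 0.05: 1 + 61.5 × 0.05 = 4.075.
- SE = 8.4 × √(4.075 × (1/600 + 1/600)) = 0.979.
- Power from the noncentral t on 22 df: 83.4%. At ICC 0.02 and 0.08 the same method gives 97.7% and 68.1%. The SAP states over 80%, 98% and 68%, so its figures reproduce.
- With 12 controls and 9 or 6 intervention schools, power at ICC 0.05 falls to 76.8% or 65.2%.

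**Possible bias.** The SAP gives no per-protocol figure, so this is an illustration. Assumptions: no true effect; only intervention schools are dropped; the schools dropped are the lowest on a delivery score that has correlation ρ with the true school mean; the school difference is stable over time; no gain from adjusting for FSM and area.

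- Between-school SD = 8.4 × √0.05 = 1.88.
- Bias = ρ × 1.88 × (mean of the top k of 12 standard normal order statistics).
- The three largest of the 12 expected values are 1.63, 1.12 and 0.79, and the next three are 0.54, 0.31 and 0.10. By symmetry, the mean of the top 9 is (1.63 + 1.12 + 0.79)/9 = 0.393, and of the top 6 is (1.63 + 1.12 + 0.79 + 0.54 + 0.31 + 0.10)/6 = 0.748.

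| ICC 0.05 | ρ = 0 | ρ = 0.3 | ρ = 0.5 | ρ = 0.8 |
|---|---|---|---|---|
| 3 of 12 dropped | 0 | 0.22 | 0.37 | 0.59 |
| 6 of 12 dropped | 0 | 0.42 | 0.70 | 1.12 |

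At ρ = −0.5 the first row becomes −0.37. At ICC 0.02 (school SD 1.19), ρ of 0.5 to 0.8 gives 0.23 to 0.37 points with 3 dropped and 0.44 to 0.71 with 6 dropped.

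Simulated t tests on school means at ICC 0.05 and ρ of 0.5 to 0.8 put the chance of a falsely significant benefit at about 5% to 9% with 3 dropped and 8% to 17% with 6 dropped, against a nominal 2.5%.

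**Does the handling of baseline matter?** Suppose the retained intervention schools are shifted by b at every wave.

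- Single arm term over all waves: the bias is b.
- Arms constrained equal at baseline, with the arm term starting afterwards: the bias is b × (1 − β), where β is the slope of the follow-up school mean on the baseline school mean. Assume the same teachers at each wave and within-teacher residual correlation 0.6. School variance is 8.4² × 0.05 = 3.53 and sampling variance 8.4² × 0.95/50 = 1.34, so β = (3.53 + 0.6 × 1.34)/(3.53 + 1.34) = 0.89. With 3 dropped, 0.11 × 0.37 = 0.04 and 0.11 × 0.59 = 0.06.
- Change from baseline by arm, with the baseline arm difference estimated freely: b cancels and the bias is 0.

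**The case against.** A reader might infer that violations arise almost only in intervention schools, that self-selected schools are then compared with near-intact controls, and that the row will exceed ITT. The documents do not support this. Section 3.1 does not equate major violations with failed delivery or place them in one arm. Section 6.6 treats shortfalls in dosage, reach and fidelity separately, as grades of implementation within the intervention arm. Control schools can violate too: Section 2.4.2 excludes "Schools that have already provided or are providing MHFA training to teachers", and a control school that took up such training during the trial could count. The size and sign of any bias depend on a correlation and a number of excluded schools that the SAP does not give.

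A reader might also infer that 6.4 makes a causal claim. The phrase "those without major protocol violation to assess the effect of outliers and protocol violation on the main outcome" covers outliers and violations together, under a sensitivity heading, and can be read as asking only whether the result changes.

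Further, ITT is primary, a CACE analysis is planned, and schools are to be graded on implementation blind to outcome. All of this stands and limits the weight of the point. But the CACE in 6.5 is at individual level, for completing the one- or two-day training, and the analysis in 6.6 compares intervention schools only with each other. Neither deals with school-level exclusion from the randomised comparison. How the primary model treats baseline is a wider question; here it matters because selection removes the protection of randomisation.

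**Conclusion.** The point holds for this sensitivity analysis. Exclusion of whole schools after randomisation is explicit, and re-use of the primary model without further correction follows from 6.2 and 6.4. Unequal exclusion by arm is likely but is an inference. Bias also requires exclusion to be related to school wellbeing; under the assumptions in the working it is about 0.2 to 0.6 points with 3 schools dropped and 0.4 to 1.1 with 6, at ICC 0.05. That is at most somewhat over a third of the 3-point target (1.12/3 = 0.37). It is zero without the correlation and negative if the correlation is negative. A single arm term over all waves is the natural reading of 6.2 and 6.3, but the SAP does not write the model out; if the term starts only after baseline, most of the bias goes. The primary ITT conclusion is not affected.

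**What to change.** In Sections 3.1 and 6.4:

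1. Estimate the per-protocol effect as change from baseline by arm: keep an arm term for the baseline difference and report the arm-by-post-baseline term. This removes a stable school difference, but not a difference in trend related to delivery.
2. Apply one list of major violations to both arms, including uptake of MHFA training by a control school. Classify schools blind to outcome, and report the schools excluded, by arm and reason.
3. Beside it, report a school-level CACE on all 24 randomised schools, with allocation as the instrument for delivery without major violation.
4. State in 6.4 that the per-protocol re-run is a non-randomised comparison and does not estimate the effect of protocol violation.

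The cost is SAP wording and one or two model runs on data already planned. The school-level CACE assumes no effect in violating schools, so it overstates the effect if delivery there was partial. For example, if 3 of 12 schools violate and still gain half the effect, the ITT effect is 0.75 + 0.25 × 0.5 = 0.875 of the full effect, and dividing by 0.75 gives 1.17 times the full effect.
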